5.6. Analyses of Efficacy Endpoints

The efficacy analyses will be performed for the following subjects on all efficacy endpoints, separately. The comparisons in all efficacy endpoints will be performed between the the REGN10933+REGN10987 2.4g and 8.0g combined dose group and placebo group as well as between each treatment group and placebo group.

- Pooled phase 3 Cohort 1 and phase 2 cohort 1A subjects
- Phase 3 Cohort 1 subjects (ie, subjects randomized after 01DEC2020 in Cohort 1)
- Phase 2 cohort 1A subjects

5.6.1. Analysis of Primary Efficacy Endpoints

5.6.1.1. Analysis of Primary Virologic Efficacy Endpoint

The primary analysis on the comparison between the the REGN10933+REGN10987 2.4g and 8.0g combined dose group and placebo with respect to the virologic endpoint of time-weighted average daily change from baseline in viral load (\log_{10} copies/mL) from day 1 to day 7 and other post-baseline visit timepoint will be performed in the Seronegative mfAS in the pooled phase 3 cohort 1 and phase 2 cohort 1A patients. The estimand for the analysis is the difference in means between the the REGN10933+REGN10987 2.4g and 8.0g combined dose group and placebo in the pooled phase 3 cohort 1 and phase 2 cohort 1A patients. Data collected after use of convalescent plasma therapy or other antispike monoclonals will be excluded from efficacy analysis. All other available data will be used in the analysis regardless of intercurrent events such as rescue medication or discontinuation, i.e., treatment policy approach.

The analysis will be based on the observed data with no imputation for missing data except as defined in Section 4.5.1.1 for viral load values that are below lower limit of detection (<LLOD), below lower limit of quantification (<LLOQ) or above upper limit of quantification (>ULOQ) of the assay.

The variable will be analyzed using the Analysis of Covariance (ANCOVA) model with treatment group and the type of background standard-of-care as fixed effects, and baseline viral load and treatment by baseline interaction as covariates.

The least squares means estimates for time-weighted average daily change from baseline in viral load for each treatment group, as well as the difference between the REGN10933+REGN10987 2.4g and 8.0g combined doses and placebo as well as between each individual dose treatment group and placebo, will be provided along with the corresponding two-sided p-value, standard error, and associated 95% confidence interval.

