9.1.3. Early Termination from the Study

Patients who are withdrawn from the study prior to day 29 will be asked to complete an early termination (ET) visit consisting of day 29 assessments and sample collections. In phase 1, patients withdrawn from the study after day 29 will be asked to complete an ET visit consisting of the EOS visit (day 169) assessments and sample collections. In phase 2, patients withdrawn from the study after day 29 will be asked to complete an ET phone visit consisting of the EOS visit (day 57) assessments.

All patients who are withdrawn from the study will be contacted by phone to obtain vital status. For patients in phase 1, this call will occur on day 169. For patients in phase 2, this will occur on day 57.

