11.4.6.1. Primary Efficacy Analyses

11.4.6.2. Analysis of Primary Virologic Efficacy Endpoint

The primary analysis on the comparison between the REGN10933+REGN10987 2.4g and 8.0g combined dose group and placebo with respect to the virologic endpoint of time-weighted average daily change from baseline in viral load (\log_{10} copies/mL) from day 1 to day 7 and other post-baseline visit timepoint will be performed in the Seronegative mFAS in the pooled phase 3 cohort 1 and phase 2 cohort 1A patients. The estimand for the analysis is the difference in means between the REGN10933+REGN10987 2.4g and 8.0g combined dose group and placebo in the pooled phase 3 cohort 1 and phase 2 cohort 1A patients. Data collected after use of convalescent plasma therapy or other anti-spike monoclonals will be excluded from efficacy analysis. All other available data will be used in the analysis regardless of intercurrent events such as rescue medication or discontinuation, ie, treatment policy approach.

The analysis will be based on the observed data with no imputation for missing data except as defined in the SAP for viral load values that are below lower limit of detection (<LLOD), below lower limit of quantification (<LLOQ) or above upper limit of quantification (>ULOQ) of the assay.

The variable will be analyzed using the Analysis of Covariance (ANCOVA) model with treatment group and the type of background standard-of-care as fixed effects, and baseline viral load and treatment by baseline interaction as covariates.

The least squares means estimates for time-weighted average daily change from baseline in viral load for each treatment group, as well as the difference between the REGN10933+REGN10987 2.4g and 8.0g combined doses and placebo as well as between each individual dose treatment group and placebo, will be provided along with the corresponding two-sided p-value, standard error, and associated 95% confidence interval.

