5.6.1.2. Analysis of Primary Clinical Efficacy Endpoints

The primary efficacy analysis will be the comparison between the the REGN10933+REGN10987 2.4g and 8.0g combined dose group and placebo in the pooled phase 3 cohort 1 and phase 2 cohort 1A patients. The primary clinical endpoint defined in Section 4.5.1.2 will be analyzed using the landmark analysis approach for day 6 through day 29, as well as analyzed for day 1 through day 29 in the order specified in Section 5.6.3.

The proportion of patients who died or went on mechanical ventilation will be analyzed using either the exact method for binomial distribution or asymptotic normal approximation method. If the number of events is small (e.g., $np \leq 5$ or $n(1-p) \leq 5$ in any treatment group, where n is the number of patients in the treatment group and p is the proportion of events), then the Fisher's exact test will be applied. Otherwise, stratified Cochran-Mantel Haenszel (CMH) test, stratified by the type of background standard-of-care (antiviral therapies and non-antiviral therapies), will be applied. Relative risk and relative risk reduction and corresponding 95% confidence intervals compared to placebo group will be estimated by Farrington-Manning method. Missing data will be considered as non-events.

The analysis will be performed for the High Viral Load mFAS, the Seronegative mFAS, and the overall mFAS.

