6.2. Data Handling Convention for Efficacy Variables

The virologic endpoint analysis will be based on the observed data with no imputation for missing data except as defined in Section 4.5.1.1 for viral load values that are below lower limit of detection (<LLOD), below lower limit of quantification (<LLOQ) or above upper limit of quantification (>ULOQ) of the assay.

In the analysis for the clinical endpoints based on proportions of patients with the event, the missing data will be considered as non-events.

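### The exclusion of data after convalescent plasma or other anti-spike antibodies is not limited to viral load, so it can remove deaths and ventilations from the primary clinical endpoint

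*SAP*

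**What the plan says.** **Exclusion.** SAP 5.6.1.1, on the primary virologic endpoint: "Data collected after use of convalescent plasma therapy or other antispike monoclonals will be excluded from efficacy analysis". Protocol 11.4.6.2 has the same sentence, "Data collected after use of convalescent plasma therapy or other anti-spike monoclonals will be excluded from efficacy analysis", and so does the synopsis. Directly before it in the SAP stands an estimand for viral load: "The estimand for the analysis is the difference in means between" the combined doses and placebo. Directly after it comes the rule for everything else: "All other available data will be used in the analysis regardless of intercurrent events such as rescue medication or discontinuation", which is labelled treatment policy.

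**Missing clinical data.** SAP 5.6.1.2, on the primary clinical endpoint: "Missing data will be considered as non-events". SAP 6.2 repeats this for every proportion endpoint: "In the analysis for the clinical endpoints based on proportions of patients with the event, the missing data will be considered as non-events". Neither section mentions plasma or other antibodies.

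**Definition of the clinical endpoint.** SAP 4.5.1.2 counts a patient who dies or reaches ordinal score 2 within the window. For day 6 to 29 it removes patients who died, were ventilated or dropped out before day 6, and no others.

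**Vital status.** Protocol 9.1.3: "All patients who are withdrawn from the study will be contacted by phone to obtain vital status".

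**The concern.** The plan has no intercurrent-event rule of its own for death or mechanical ventilation. The only such rules are in the virologic paragraph, and one of them is worded for efficacy analysis at large. A programmer who takes that wording at face value would cut clinical data at the first plasma or antibody dose. What follows is then missing, and missing means no event. A known death would leave the numerator while the patient stayed in the denominator.

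Such therapy would start after randomization and could well be given to patients who are getting worse, so the events removed need not be a random sample. The question affects all six clinical hypotheses (orders 2 to 7 in SAP Table 9). If it is settled after unblinding, that part of the pre-specification is lost.

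**Working it through.** **1. How far the wording reaches.** The neighbouring sentences in SAP 5.6.1.1 refer to the analysis at hand. The exclusion sentence instead refers to efficacy analysis. Under the heading Efficacy Analysis, SAP 1.1 and Protocol 11 describe both the viral-load endpoint and death or ventilation. SAP 5.6 and Protocol 11.4.6 use the plural for all efficacy endpoints. By the plan's own usage, then, the term covers the clinical endpoint.

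**2. What a programmer could do with a patient who dies on day 15 after plasma on day 10.**
- Follow SAP 4.5.1.2 alone: event.
- Apply the exclusion and treat the removed data as missing: non-event, still in the denominator.
- Apply the exclusion by removing the patient: in neither numerator nor denominator.

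No section says which to use. The step from excluded to missing is not written down either.

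**3. The plan's own figures.** None is disputed. The 35.8% reduction used below is the phase 3 planning effect (HR 0.642, 241 events, 90% power, Protocol 11.2.3). Schoenfeld's formula at 2:1 reproduces it: (1.960 + 1.282)² / [(1/3)(2/3)(ln 0.642)²] = 241. The final-analysis thresholds (29.0%, 41.2% and 36.6% at a 13.1% placebo risk, SAP 2.3) come without the mFAS sizes. Solving z = (p0 − p1) / √[p̄(1 − p̄)(1/n0 + 1/n1)] = 1.96 at 2:1 implies totals of about 1132 (overall), 511 (seronegative) and 671 (high viral load). All are below the 755 + 609 = 1364 randomized.

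**4. The three readings in numbers.** Assumed, not in the documents: a share u of patients receives such therapy, with a 40% event risk afterwards. Overall risk is 13.1%.
- u = 5%: counted 13.1%; scored event-free 13.1 − 0.05 × 40 = 11.1%; patient removed 11.1 / 0.95 = 11.7%.
- u = 1%: 13.1%; 12.7%; 12.7 / 0.99 = 12.8%.

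Under event-free scoring, with about 170 placebo and 340 active seronegative patients, the smallest significant reduction moves from 41.2% to 44.5% (u = 5%) or 41.8% (u = 1%).

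**5. Direction.** Let f0 and f1 be the shares of placebo and active events that are removed (assumed). Observed RR = true RR × (1 − f1) / (1 − f0). For example, 0.642 × 0.95 / 0.90 = 0.678, a reduction of 32.2%. Power is for a single overall-mFAS test with N = 1132 (implied), 2:1, placebo risk 13.1% and true reduction 35.8%.

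| f0 / f1 | Observed reduction | Power |
|---|---|---|
| 0 / 0 | 35.8% | 68.8% |
| 10% / 10% | 35.8% | 64.0% |
| 20% / 20% | 35.8% | 58.8% |
| 10% / 5% | 32.2% | 54.5% |
| 20% / 10% | 27.8% | 38.4% |
| 5% / 10% | 39.2% | 74.8% |
| 10% / 20% | 42.9% | 80.5% |

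With no true effect, 10% / 20% gives an apparent reduction of 1 − 0.80/0.90 = 11.1%, and 20% / 10% an apparent increase of 0.90/0.80 − 1 = 12.5%. Equal removal costs power only. If the exclusion covers viral load alone, every row returns to the first.

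**The case against.** The strongest reply is placement. The sentence appears only under the virologic endpoint, between a difference-in-means estimand and a no-imputation rule for viral load. The clinical endpoint has its own sections (SAP 5.6.1.2, Protocol 11.4.6.3), which neither repeat nor cite it. SAP 4.5.1.2 counts these events, and its list of exclusions does not include plasma. SAP Table 6 takes deaths for the secondary endpoint from any CRF. This stands, and it rules out one stronger reading: a reader might infer that the plan definitely scores a death after plasma as a success. No section says that. No section says the opposite either, and the broad term remains.

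A second reply is that use should be rare. Prior or planned use is an exclusion criterion (Protocol 7.2.2), and on-study use is not permitted (Protocol 8.10.1, SAP 4.4). So 5% may be too high. Convalescent serum is nevertheless on the list of recorded medications (Protocol 9.2.3.3), and the sponsor saw enough need to write a rule. Blinding also limits the scenarios: if the drug had no effect at all, nothing in the documents would make use differ by arm except chance. The unequal rows matter mainly when the drug changes the clinical course.

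Three further inferences fail:
- The treatment-policy label might look contradictory. It is in the following sentence and covers only the remaining data.
- A patient who withdraws on day 2 might seem to count as event-free in every clinical test. Drop-outs before day 6 leave the day 6 to 29 tests altogether, so this can arise only in the day 1 to 29 tests (orders 5 to 7).
- Deaths learned from the post-withdrawal call might seem lost. A known death is not missing, and SAP 4.5.1.2 would count it. The plan merely does not say how that call feeds the endpoint.

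**Conclusion.** The concern holds as a gap in scope. The exclusion as worded reaches the primary clinical endpoint, the endpoint definition points the other way, and nothing reconciles them. If the exclusion were applied there, real deaths and ventilations would be scored as event-free or their patients dropped, in any of the six clinical tests. The bias could favour either group.

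The size cannot be stated, because the documents give neither the rate of such therapy nor the risk after it. The figures above show only what assumed rates would do: from almost nothing at 1% use to several points of relative reduction when removal differs by arm. They also rest on mFAS sizes implied by the stated thresholds.

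Separately, counting truly unknown status as a non-event understates risk in the day 1 to 29 tests. That is the lesser issue. It does not justify replacing the primary proportion by a Kaplan-Meier estimate, because censored time-to-event analyses of the same composite are already planned (SAP Table 7 and 5.6.2.2).

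**What to change.** Before database lock:

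1. In SAP 5.6.1.1, Protocol 11.4.6.2 and the synopsis, restrict the exclusion to viral-load measurements collected after convalescent plasma or another anti-spike antibody.
2. In SAP 5.6.1.2 and 6.2, state that every known death or mechanical ventilation in the window counts, regardless of other therapy or withdrawal. Say that all collected vital status is used, including the post-withdrawal call in Protocol 9.1.3.
3. For status that is truly unknown in the day 1 to 29 tests, add a tipping-point sensitivity analysis beside the Kaplan-Meier analyses already planned. It should show how many unknown outcomes, by arm, would have to be events to change the conclusion.

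The cost is a few sentences in two documents and minor programming. No new data are needed, and the hierarchy and the primary test stay as they are.

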5.6.1.2. Analysis of Primary Clinical Efficacy Endpoints

The primary efficacy analysis will be the comparison between the the REGN10933+REGN10987 2.4g and 8.0g combined dose group and placebo in the pooled phase 3 cohort 1 and phase 2 cohort 1A patients. The primary clinical endpoint defined in Section 4.5.1.2 will be analyzed using the landmark analysis approach for day 6 through day 29, as well as analyzed for day 1 through day 29 in the order specified in Section 5.6.3.

The proportion of patients who died or went on mechanical ventilation will be analyzed using either the exact method for binomial distribution or asymptotic normal approximation method. If the number of events is small (e.g., $np \leq 5$ or $n(1-p) \leq 5$ in any treatment group, where n is the number of patients in the treatment group and p is the proportion of events), then the Fisher's exact test will be applied. Otherwise, stratified Cochran-Mantel Haenszel (CMH) test, stratified by the type of background standard-of-care (antiviral therapies and non-antiviral therapies), will be applied. Relative risk and relative risk reduction and corresponding 95% confidence intervals compared to placebo group will be estimated by Farrington-Manning method. Missing data will be considered as non-events.

The analysis will be performed for the High Viral Load mFAS, the Seronegative mFAS, and the overall mFAS.

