- Other therapies (immune-based therapies, both antiviral and immune-based therapies, or no COVID-19-specific treatment)

Phase 2/3

In phase 2/3, patients were randomized in a 1:1:1 allocation ratio to one of the following treatment groups:

- Co-administered REGN10933+REGN10987 combination therapy 2.4 g (1.2 g of REGN10933 plus 1.2 g of REGN10987) IV single dose
- Co-administered REGN10933+REGN10987 combination therapy 8.0 g (4.0 g of REGN10933 plus 4.0 g of REGN10987) IV single dose
- Placebo IV single dose

Randomization in phase 2/3 was stratified by country and type of background standard-of-care being administered for COVID-19 at randomization as follows:

- Antiviral therapies (remdesivir or other)
- Non-antiviral therapies (immune-based therapies, both antiviral and immune-based therapies, or no COVID-19-specific treatment)

The enrollment into Cohorts 2 and 3 were paused based on a recommendation from the IDMC (initial IDMC recommendation on 30 October 2020).

Most of the patients in the study were enrolled in the United States. Other countries where patients were enrolled in the study include Romania, Brazil, Chile, Mexico, and Moldova.

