5.6.3. Adjustment for Multiple Comparisons

Multiplicity Considerations

The following multiplicity adjustment approach, a hierarchical procedure, will be used to control the overall Type-1 error rate at 0.05 for the primary virologic and clinical outcome endpoints in comparison between the combined doses of REGN10933+REGN10987 treatment group and placebo group in the pooled phase 3 cohort 1 and phase 2 cohort 1A patients. Each hypothesis will be formally tested only if the preceding one is significant at the 2-sided 0.05 significance level. The hierarchical testing order is shown in [Table 9](#).

Table 9: Hierarchical testing order

Type	Description	Testing Order
Primary virologic outcome	Time-weighted average change from baseline viral load in NP sample through day 7 in seronegative mFAS for comparing the combined doses of REGN10933+REGN10987 versus placebo	1
Primary clinical outcome	Proportion of patients who died or went on mechanical ventilation from day 6 to day 29 in High Viral Load mFAS for comparing the combined doses of REGN10933+REGN10987 versus placebo	2
	Proportion of patients who died or went on mechanical ventilation from day 6 to day 29 in Seronegative mFAS for comparing the combined doses of REGN10933+REGN10987 versus placebo	3
	Proportion of patients who died or went on mechanical ventilation from day 6 to day 29 in overall mFAS for comparing the combined doses of REGN10933+REGN10987 versus placebo	4
	Proportion of patients who died or went on mechanical ventilation from day 1 to day 29 in High Viral Load mFAS for comparing the combined doses of REGN10933+REGN10987 versus placebo	5
	Proportion of patients who died or went on mechanical ventilation from day 1 to day 29 in Seronegative mFAS for comparing the combined doses of REGN10933+REGN10987 versus placebo	6
	Proportion of patients who died or went on mechanical ventilation from day 1 to day 29 in overall mFAS for comparing the combined doses of REGN10933+REGN10987 versus placebo	7

All other analyses for virologic and clinical endpoints will be reported descriptively for each individual cohort and for pairwise comparison of each REGN10933+REGN10987 dose group (2.4 g IV or 8.0 g IV) versus placebo.

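### The small-count rule for the primary clinical tests can be read as counting events in a single dose arm, which would switch the combined-dose comparison to an unstratified Fisher test when neither compared group is small

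*SAP*

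**What the plan says.** SAP 5.6.1.2 makes the combined 2.4 g and 8.0 g doses versus placebo the primary clinical comparison. It then chooses the test by event counts. The switch occurs if np or n(1-p) is 5 or less "in any treatment group, where n is the number of patients in the treatment group and p is the proportion of events". In that case the analysis moves to Fisher's exact test, for which no strata are mentioned; in all other cases it is a CMH test with background standard of care as the stratum. The threshold is introduced with e.g., so it is an example and not a fixed limit. Protocol 11.4.6.3 and the protocol synopsis carry the same rule.

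The documents use the term treatment group in two ways:

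- **Single arms.** SAP 2.1 says "In phase 2/3, patients were randomized in a 1:1:1 allocation ratio to one of the following treatment groups" and lists 2.4 g, 8.0 g and placebo. SAP 5.6 distinguishes the "combined dose group and placebo group as well as between each treatment group and placebo group". SAP 5.6.1.1 likewise calls each individual dose a treatment group.
- **Combined doses.** SAP 5.6.3 controls type I error "in comparison between the combined doses of REGN10933+REGN10987 treatment group and placebo group".

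The testing sequence is strict: "Each hypothesis will be formally tested only if the preceding one is significant at the 2-sided 0.05 significance level".

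**The concern.** With p the observed proportion, np is simply the number of events. If the rule looks at each dose arm, a test between two large groups is chosen by a count in half of one of them. The purpose of a small-count rule, to avoid a normal approximation where it fails, does not apply when both compared groups have well over 5 events.

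Three consequences follow on that reading. Fisher's test is conservative, so power is lost. The background standard-of-care stratum, which was used in randomization, drops out of the test. And the switch becomes likelier as the drug works better, because each dose arm then has fewer events. Since the hierarchy stops at the first non-significant step, a needless switch at step 2 or 3 could end formal testing on data that CMH would call significant.

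Even without a view on which reading was meant, two programmers could follow this SAP and run different confirmatory tests.

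**Working it through.** **1. The comparison the plan was powered for.** Protocol 11.2.3 gives 241 events for 90% power at two-sided 0.05 and HR 0.642. With 2:1 allocation the Schoenfeld formula is (1.960+1.282)² / [(1/3)(2/3)(ln 0.642)²] = 10.51 / (0.2222 × 0.1964) = 241. The figure reproduces, so the planned comparison is combined doses versus placebo.

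**2. Arm sizes.** The documents do not give the sizes of the analysis sets. SAP 2.3 gives minimal significant reductions of 41.2% (Seronegative), 36.6% (High Viral Load) and 29.0% (overall) at a 13.1% placebo rate. With pooled variance and 2:1 allocation, n per arm = 1.96² × p̄(1-p̄) × 1.5 / (p0-p1)².

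- Seronegative: p1 = 0.131 × 0.588 = 0.0770, p̄ = 0.0950, n = 3.8416 × 0.0860 × 1.5 / 0.0540² = 170.
- High Viral Load: p1 = 0.131 × 0.634 = 0.0831, p̄ = 0.0990, n = 224.
- Overall: n = 377, or 1132 in total, which fits within the 755 + 609 = 1364 randomized.

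Unpooled variance gives larger sets (591, 762 and 1246 in total), which would make the switch rarer.

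**3. A table that flips.** Take 13/340 on the combined doses and 14/170 on placebo, a reduction of 54%. Expected events on active are 340 × 27/510 = 18. The Mantel-Haenszel variance is 340 × 170 × 27 × 483 / (510² × 509) = 5.69. Chi-square = (13-18)²/5.69 = 4.39, p = 0.036. Fisher gives p = 0.057. If the 13 events split 5+8, the single-arm reading uses Fisher. If they split 6+7, it uses CMH. The combined table is the same in both cases. Likewise 12/340 versus 13/170 gives 0.043 and 0.051.

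**4. How often, and at what cost.** Steps 2 to 4 use day 6-29. SAP 4.5.1.2 removes patients with events before day 6, so these counts are lower than for day 1-29, but no day 6-29 rate is given. I assumed a placebo rate of 6.5% or 8% and enumerated all three-arm outcomes exactly in a single stratum. The three values in each cell are for true reductions of 40%, 50% and 60%.

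| Test | n/arm | Placebo rate | Fisher used, single-arm reading (%) | CMH power (%) | Power lost (points) |
|---|---|---|---|---|---|
| 3, Seronegative, day 6-29 | 170 | 6.5% (assumed) | 59 / 78 / 92 | 26.1 / 39.7 / 56.5 | 3.0 / 4.4 / 5.4 |
| 3 | 170 | 8% (assumed) | 32 / 54 / 79 | 31.3 / 47.0 / 64.8 | 1.8 / 2.9 / 3.8 |
| 2, High Viral Load, day 6-29 | 224 | 6.5% (assumed) | 24 / 46 / 72 | 33.1 / 49.6 / 67.6 | 1.4 / 2.4 / 3.2 |
| 2 | 224 | 8% (assumed) | 8 / 21 / 48 | 39.0 / 58.1 / 76.8 | 0.4 / 0.8 / 1.4 |
| 6, Seronegative, day 1-29 | 170 | 13.1% (SAP 2.3) | 1 / 6 / 22 | 47.3 / 68.4 / 85.9 | 0.04 / 0.13 / 0.27 |
| 5, High Viral Load, day 1-29 | 224 | 13.1% (SAP 2.3) | 0.1 / 0.6 / 4 | 57.9 / 79.4 / 93.3 | 0.00 / 0.00 / 0.01 |

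The pattern follows from the expected counts. At 6.5% and a 50% reduction, a Seronegative dose arm expects 170 × 0.0325 = 5.5 events. At 13.1% and a 41.2% reduction it expects 170 × 0.0770 = 13.

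For overall mFAS (377 per arm) the loss is about 0.1 points at most at a 6.5% rate and zero at 13.1%. Stratified simulations agree with the table. The worst case was 6.5 points at step 3, with a 6.5% rate, a 60% reduction and 30% of patients in a stratum at three times the risk.

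**5. The rule applied to the two compared groups.** Fisher is then used in at most about 15% of trials in the scenarios above, and power is within 0.1 point of CMH in all of them.

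**6. Type I error.** Under the null, rejection in the drug's favour was never higher with the single-arm rule than with always-CMH. At 170 per arm and 6.5%, for example, it was 0.0266 against 0.0286. The switch errs on the conservative side.

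**The case against.** A reader might infer that the plan definitely runs Fisher whenever one dose arm has 5 or fewer events, and that all of tests 2 to 7 lose power as a result. The documents do not support that. SAP 5.6.1.2 opens by defining the comparison as combined doses versus placebo, so the term can mean either of those two groups. SAP 5.6.3 uses it that way, and on that reading the problem all but disappears. The threshold is only an example.

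On size, the only documented rate is 13.1% for day 1-29, where the loss is negligible. At that rate most triggered Seronegative trials stay significant under Fisher (87-98%). The losses of several points need a day 6-29 rate that the documents do not give. They also depend on treating 13.1% as a placebo rate. SAP 2.3 says it equals the blinded proportion, so if the drug works the true placebo rate is higher. Using 13.1% as the blinded rate, with 40-60% of events on day 6-29, gives losses of 0.2-3.0 points at step 3 and up to 0.9 at step 2. The flipping tables are chosen near 0.05.

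All of this stands as a limit on the size. It does not remove the defect. SAP 2.1, 5.6 and 5.6.1.1 favour the single-arm reading, day 6-29 counts must be lower than day 1-29 counts, and choosing a reading after unblinding would be a data-driven choice of the confirmatory test.

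**Conclusion.** The concern holds as an ambiguity whose more natural reading gives a poor rule. On that reading the confirmatory test can depend on how the combined-dose events split between the two doses, and it becomes an unstratified, conservative test when neither compared group is small.

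The exposure is mainly step 3, then step 2. It is about 2-5 points of power at step 3 and 0.4-3 at step 2, given back-solved arms of 170 and 224, an assumed day 6-29 placebo rate of 6.5-8% and true reductions of 40-60%. It is at most 0.3 points at 13.1%, and essentially nil for the overall-mFAS tests 4 and 7. There is no false-positive risk. This should be corrected, but it does not threaten the validity of a positive result.

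**What to change.** Before unblinding, in SAP 5.6.1.2, Protocol 11.4.6.3 and the matching synopsis text:

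1. Apply the rule to the two groups being compared, which for tests 2 to 7 are the combined doses and placebo.
2. Delete the e.g. so that the threshold of 5 is fixed.
3. When the rule is triggered, use an exact test stratified by background standard of care in place of unstratified Fisher.

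The cost is one sentence in each place and no new data. Items 1 and 2 keep power within 0.1 point of CMH in every scenario checked. Item 3 keeps the standard-of-care randomization factor in the test. Its own power was not calculated here, but it would apply only in the minority of trials where a compared group really has few events.
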